8.1 Summary of adverse events

All of the following will be presented by participants producing a successful swallow at first test, participants producing a successful swallow at repeat test, overall (first and repeat test combined, with only AEs from the repeat test contributing for participants who had two tests) and in total (both first and repeat test counted as separate instances).

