3.2.4 Safety population

The safety analysis will look at all participants attempting to swallow a Cytosponge™: both the ones producing a Cytosponge™ sample ('successful swallows'), independently from the test result, and the ones not able to swallow a sponge. The endpoints related to the safety of the Cytosponge™, i.e. total number of AEs, number of AEs per participant, number/proportion of participants experiencing an AE, will be analysed on this population.

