8.1.2 Number of patients affected by an adverse event

We will report on total number of patients affected by an AE up to 7 days after receiving the test and their proportion over the number of patients who swallowed a Cytosponge™ successfully.

As patients can experience more than one AE, we will also show the median number and range of AEs per participant.

Number and distribution of patients affected by AEs will be presented by site. Median/range by site should also be presented.

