8.3 Summary of Serious Adverse Events (SAE)

As for the above, SAEs will only be listed for responders of the Cytosponge™. They will be presented individually stating the participant ID, the event narrative, and the relationship with having undertaken the Cytosponge™.

An example of this is available in the DMC report from October 2018:

BEST3 SOP 008 – BEST3 Statistical Analysis Plan v1.0. [If this SAP has been printed or saved electronically, please check Sharepoint to ensure this version is the most up-to-date.](#)

CPTU Template Creating and Revising SOPs and other Guidelines v11.0 05/Jul/2019

[G:\EMS\CPTU\BEST3\Section 17 TRIAL COMMITTEES\Data Monitoring Committee \(DMC\)\Meetings \(agenda and minutes\)\4. DMC meeting - 30 October 2018\BEST3 DMC Report - Open - 30 October 2018.pdf](G:\EMS\CPTU\BEST3\Section 17 TRIAL COMMITTEES\Data Monitoring Committee (DMC)\Meetings (agenda and minutes)\4. DMC meeting - 30 October 2018\BEST3 DMC Report - Open - 30 October 2018.pdf)

Number/proportion of SAE (out of all successful swallows) will be reported.

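### The SAP defines safety in everyone who attempts a swallow but tabulates AEs only in successful swallowers, and no tally counts each participant once across all tests

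*SAP*

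**What the plan says.** Section 3.2.4 (Safety population) states: "The safety analysis will look at all participants attempting to swallow a Cytosponge™". It names both those who produce a sample, "independently from the test result, and the ones not able to swallow a sponge". It then ties specific endpoints to that group: total AEs, AEs per participant, and "number/proportion of participants experiencing an AE, will be analysed on this population".

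Section 8 uses other groups for the same endpoints:

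- Section 8.1 opens with "All of the following will be presented by participants producing a successful swallow at first test", and continues with successful swallows at the repeat test, an 'overall' tally and an 'in total' tally.
- The 'overall' tally is described as "first and repeat test combined, with only AEs from the repeat test contributing for participants who had two tests". The 'in total' tally counts a participant's two tests separately.
- Section 8.1.1 limits AE counts, up to 7 days after the test, to successful swallowers.
- Section 8.1.2 reports the number of affected patients and their "proportion over the number of patients who swallowed a Cytosponge" with success.
- Section 8.3 lists SAEs individually for responders, then states "Number/proportion of SAE (out of all successful swallows) will be reported".

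**The concern.** Two separate matters are at stake.

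The first is a contradiction about population. The SAP gives two incompatible groups for the same AE endpoints. If Section 8 is followed, someone who has an AE during an unsuccessful attempt and never swallows the device is missing from every AE summary, although Section 3.2.4 expressly includes that person. Safety is a named secondary endpoint (item 10 in Section 2.2), and tolerability in people who cannot complete the procedure is part of it.

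The second is the rule for combining tests. Letting the repeat replace the first test suits sample adequacy, where Sections 2.3 and 4.1 use it, because a later result supersedes an earlier one. A harm at the first test is not superseded by an uneventful second one. A per-participant figure read from 'overall' would class some affected participants as unaffected.

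**Working it through.** The SAP contains no AE rate, failed-swallow share or repeat-test share, so there is no safety figure to reproduce. The check is mainly a comparison of the text.

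**Step 1: who is counted where.**

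| Section | Item | Group used |
|---|---|---|
| 3.2.4 | Total AEs, AEs per participant, number/proportion with an AE | All who attempt, including those unable to swallow |
| 8.1, 8.1.1 | AE summaries and counts | Successful swallowers |
| 8.1.2 | Denominator for participants affected | Successful swallowers |
| 8.3 | SAE listing | Responders |
| 8.3 | SAE denominator | Successful swallows |

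The first row cannot be reconciled with the second and third. The SAE listing and its denominator also differ: Section 4.1 counts as responders both the interested and the not interested, and treats attenders as including people who come but cannot swallow.

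**Step 2: what each AE tally gives for a participant with two successful swallows, an AE at the first test and none at the repeat.**

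| Tally in 8.1 | Is the event shown? | Is each participant counted once across all tests? |
|---|---|---|
| First test | Yes | No, first test only |
| Repeat test | No | No, repeat test only |
| Overall | No | Counted once, but as AE-free |
| In total | Yes | No, counted as two instances |

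The event is not lost from the report. But no tally gives the number of distinct participants with at least one AE after any test.

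**Step 3: how large the 'overall' shortfall could be, under assumptions.** Let r be the share of tested participants who have a repeat test and p the AE probability per test. Assume at most one AE per test, the same p at both tests, and independence between tests. The values of r and p are assumed, not taken from the SAP.

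- Share of AEs missed. Expected AEs per participant are (1 + r)p, and 'overall' counts p, so the share missed is r/(1 + r). For r = 5%, 10% and 15%: 0.05/1.05 = 4.8%, 0.10/1.10 = 9.1%, 0.15/1.15 = 13.0%.
- Share of affected participants missed. The true proportion is (1 - r)p + r[1 - (1 - p)²] and 'overall' gives p. The share missed is 1 - p/{(1 - r)p + r[1 - (1 - p)²]}. For r = 10% and p = 10% the true proportion is 0.1090 against 0.1000, so 8.3% are missed.

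| r | AEs missed | Affected participants missed, p = 2% | p = 10% | p = 30% |
|---|---|---|---|---|
| 5% | 4.8% | 4.7% | 4.3% | 3.4% |
| 10% | 9.1% | 8.9% | 8.3% | 6.5% |
| 15% | 13.0% | 12.8% | 11.9% | 9.5% |

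Any AE in a person who never swallows is missed in addition, and from all four tallies.

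**The case against.** AE and SAE reporting here is descriptive, with no statistical analysis planned (Sections 8.2 and 8.4). Section 8.1 asks for four tallies, so an attentive reader can see first-test events in two of them. All of that stands, and it limits the second matter to the 'overall' tally and to per-participant figures drawn from it.

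A reader might go further in several ways that the SAP does not support:

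- *That first-test AEs in re-tested participants are deleted.* They remain in the 'first test' and 'in total' tallies.
- *That the 'overall' rule breaches the safety population.* Section 3.2.4 does not say how two tests are to be combined. The rule is a poor tally definition; only the restriction to successful swallowers conflicts with Section 3.2.4.
- *That all safety reporting excludes failed swallowers.* The SAE listing covers responders, and a responder who fails to swallow falls within that wording.
- *That leaving out failed swallowers must make the device look safer.* It removes them from numerator and denominator alike. In an invented example with AEs in 10 of 100 swallowers and 0 of 10 failures, including the failures moves the proportion from 10% to 10/110 = 9.1%. Only the AE count has a certain direction. For SAEs, a numerator drawn from responders over successful swallows could even overstate the proportion.
- *That a head count can be attached.* Applying the 24.0% uptake in Section 2.5.3 to half of the 13,234 participants gives 0.24 × 6,617 ≈ 1,588 people. The SAP does not say whether that uptake means attending or swallowing, and gives no failure or re-test share. The number re-tested would in any case not be the number with a first-test AE.

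None of this removes the conflict between Section 3.2.4 and Section 8, or supplies the missing per-participant tally.

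**Conclusion.** The point holds in two limited parts. The SAP contradicts itself on the population for the AE endpoints, and Section 8.3 mixes two groups for SAEs. This can be read directly from the text. As Section 8 stands, AEs in people who never swallow appear in no AE tally, so AE counts can only be too low; the effect on the proportion affected is of unknown sign and size.

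The 'overall' rule misclassifies participants whose only AE came at a first test that was later repeated, and no other tally gives the per-participant figure. For this part the direction is downward. The size rests wholly on assumption: about 5-13% of AEs, and about 3-13% of affected participants, for re-test shares of 5-15%, per-test AE probabilities of 2-30%, and independent tests of equal risk.

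This should be corrected before the tables are produced. It does not touch the primary endpoint.

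**What to change.** - Use the Section 3.2.4 population, all who attempted, for AE and SAE numerators and denominators throughout Section 8.
- Show participants with a failed swallow as a separate row, so that results in successful swallowers can still be read.
- Define 'overall' as any AE after any attempt, first or repeat. Count each participant once for the proportion affected, and every event for the AE count.
- Keep the first-test and repeat-test tallies, and label 'in total' as a per-test figure.

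The cost is rewording in Sections 8.1 to 8.1.2 and 8.3 and a change to the table shells; no analysis method changes. Section 3.2.4 implies that AEs are recorded for people unable to swallow, but the SAP does not say so outright. This should be confirmed, and any gap in their AE collection reported with the tables.

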8.1.1 Number of adverse events

AEs up to 7 days after receiving the test for participants successfully swallowing the Cytosponge™ test will be presented:

- by type: number and distribution
- by severity (severe, moderate, mild): number and distribution
- by study site: number and distribution; median/range by site
- overall: total number

An example of this is available in the DMC report from October 2018:

[G:\EMS\CPTU\BEST3\Section 17 TRIAL COMMITTEES\Data Monitoring Committee \(DMC\)\Meetings \(agenda and minutes\)\4. DMC meeting - 30 October 2018\BEST3 DMC Report - Open - 30 October 2018.pdf](G:\EMS\CPTU\BEST3\Section 17 TRIAL COMMITTEES\Data Monitoring Committee (DMC)\Meetings (agenda and minutes)\4. DMC meeting - 30 October 2018\BEST3 DMC Report - Open - 30 October 2018.pdf)

8.1.2 Number of patients affected by an adverse event

We will report on total number of patients affected by an AE up to 7 days after receiving the test and their proportion over the number of patients who swallowed a Cytosponge™ successfully.

As patients can experience more than one AE, we will also show the median number and range of AEs per participant.

Number and distribution of patients affected by AEs will be presented by site. Median/range by site should also be presented.

8.2 Analysis of adverse events

No statistical analysis of AEs is planned due to the fact that there is no comparison between study arms. However, we may choose to report some of the figures on AEs by subgroup, such as age group, gender, BMI, smoking history, etc.

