2.4 Level of significance

The level of significance that will be used in all the statistical analyses is 5%, two-sided. However, 95% confidence intervals will be preferred to p -values in the final report.

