7.1.2 Analysis of secondary endpoints

For the sake of simplicity, the cluster design of part of the Trial will be ignored for the analysis of secondary endpoints.

Any endpoints using data on BE diagnoses will rely on *actual* data available from the Trial, i.e. the methods used for data collection for the primary endpoint will not apply.

The analysis of the secondary endpoints will be further detailed in a separate supplementary SAP.

Using data from the intervention arm *only*:

- 1) Diagnostic accuracy of the Cytosponge™ according to endoscopic findings:
PPVs will be presented with 95% Clopper-Pearson (exact) confidence intervals overall, by age group/sex, by duration of acid-suppressant medication prescriptions prior to baseline and by number of columnal cells present on the sponge.
In Stata, these can be calculated using the command `diagt` or `diagti`. In R, the function `epi.tests` should be used.
- 2) Diagnostic accuracy of the Cytosponge™ test according to endoscopic and pathology findings, i.e. by score of BE severity:
PPV will be presented with a 95% exact confidence interval.
- 3) Performance of Cytosponge™ in detecting IM of the gastric cardia:
PPV will be presented with a 95% exact confidence interval.
- 4) Performance of Cytosponge™ in detecting BE or IM of the gastric cardia:
PPV will be presented with a 95% exact confidence interval.
- 5) Performance of Cytosponge™ in detecting EAC and gastric cancer:
PPV will be presented with a 95% exact confidence interval;
Numbers needed to examine (by Cytosponge™) to detect one OAC or one HGDB will also be calculated.
- 6) Sampling adequacy:
Inadequacy rate will be presented with a 95% exact confidence interval.
- 7) Endoscopy referral rates for adequate test results and successful Cytosponge™ swallows:
The two proportions will be presented with a 95% exact confidence interval.
- 8) Patient acceptability of Cytosponge™:
Proportions will be presented with a 95% exact confidence interval.
Median number of attempts to swallow per patient will be presented with interquartile range (IQR) and range.
At baseline:
 - Measures will be presented with median, IQR and range*At day 7-14:*
 - Measures will be presented with median, IQR and range
 - Differences in STAI-6 scores at day 7-14 and baseline will be compared with a Wilcoxon signed-rank test.
- 9) Physician/nurse acceptability of Cytosponge™: qualitative outcome.
- 10) Safety of Cytosponge™:

See Section 8.

11) Performance of repeat Cytosponge™ test:

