8.4 Analysis of SAE

SAEs are expected to be a rare occurrence in the Trial, so no statistical analysis is planned.

9. Presentation of analysis

Two statisticians will work on the statistical analysis to ensure its reliability: one will write the code, the other one will review it.

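### Safety proportions get no confidence interval, and neither reason given (no arm comparison, rare SAEs) justifies leaving it out

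*SAP*

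**What the plan says.** SAP section 2.2 lists safety as secondary endpoint 10, and item 10 of section 7.1.2 refers it to section 8 without naming a method.

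Section 8 plans descriptive output:
- **AEs (8.1.2):** "We will report on total number of patients affected by an AE up to 7 days after receiving the test and their proportion", with successful swallowers as the denominator.
- **SAEs (8.3):** individual listings with narrative and relationship to the test, and "Number/proportion of SAE (out of all successful swallows) will be reported".

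It then excludes anything further, with a reason each time:
- **AEs (8.2):** "No statistical analysis of AEs is planned due to the fact that there is no comparison between study arms".
- **SAEs (8.4):** "SAEs are expected to be a rare occurrence in the Trial, so no statistical analysis is planned".

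Elsewhere the plan favours intervals. Section 2.4 says that "95% confidence intervals will be preferred to" p-values in the final report. In section 7.1.2, item 6 says "Inadequacy rate will be presented with a 95% exact confidence interval" and item 7 says "The two proportions will be presented with a 95% exact confidence interval". Both items use intervention-arm data only.

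**The concern.** A comparator is needed to test or estimate a difference between arms. It is not needed to put an interval on a single proportion, and the plan does exactly that for other endpoints with no control group. Under item 8, for example, the proportion who fail to swallow gets an exact interval, while the proportion with an SAE among much the same people does not.

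Rarity points the other way. With no events or very few, the point estimate is at or near zero whatever the sample size, and the upper limit shows what the data rule out. A report following section 8 literally would print a proportion at or near zero and leave readers to work out its precision.

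**Working it through.** **The plan's own figure.** The SAP gives no precision figure for safety. Its only design figure, 6764 (3382 per arm) for the primary endpoint, reproduces with a two-sided 5% test at 90% power. The intervention-arm rate is 0.27 × (0.04 × 0.85 + 0.15 × 0.1 × 0.06) + 0.73 × 0.1 × 0.06 = 0.013803. Against 0.006 this gives 3382 per arm (3384 if the rate is rounded to 0.0138). Nothing below depends on it.

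**Inputs for the illustration**
- Recruited: 13,234 (section 2.5.2, June 2019).
- Allocation: 1:1 (section 2). An even split of participants is an assumption, since part of the trial randomised practices.
- Uptake: 24.0% (section 2.5.3), read here as the share of invitees who reach the test.
- Level: two-sided 95%, in line with section 2.4.

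**Number tested.** 13,234 × 0.5 = 6617 invited, and 6617 × 0.24 ≈ 1588. For a range, take 45% to 55% of participants in the intervention arm (assumed) and uptake of 21% to 27% (the span of the table in section 2.5.3):
- low: 13,234 × 0.45 × 0.21 ≈ 1250
- high: 13,234 × 0.55 × 0.27 ≈ 1965

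**Exact limits.** For k participants with an event out of n, the Clopper-Pearson upper limit is the 0.975 quantile of Beta(k + 1, n − k). For k = 0 it is 1 − 0.025^(1/n), close to 3.689/n. With n = 1588, 3.689/1588 ≈ 0.0023.

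| SAEs (participants) | Point estimate, n = 1588 | Exact 95% interval, n = 1588 | Upper limit, n = 1250 | Upper limit, n = 1965 |
|---|---|---|---|---|
| 0 | 0% | 0 to 0.232% | 0.295% | 0.188% |
| 1 | 0.06% | 0.002% to 0.350% | 0.445% | 0.283% |
| 2 | 0.13% | 0.015% to 0.454% | 0.577% | 0.367% |

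Zero SAEs among 1588 would therefore leave open a true risk of about 1 in 430 (1/0.00232).

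**Denominator and counting rule.** An interval needs a defined numerator and denominator, and the SAP does not settle either:
- **Denominator.** Section 3.2.4 defines the safety population as everyone who attempts to swallow, including those who fail, and assigns the AE endpoints to it. Sections 8.1 to 8.3 restrict the AE summaries and the SAE proportion to successful swallows.
- **Numerator.** In section 8.1, the overall summary takes only repeat-test AEs for anyone tested twice, so their first-test events drop out. The in-total summary keeps them but counts tests rather than people. Neither gives the proportion of participants with an event at any test.
- **Unit.** The SAE wording in section 8.3 can be read as counting events rather than participants.

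**The case against.** Descriptive safety reporting is a legitimate choice, and the sentence in 8.2 may mean only that no between-arm inference is planned. Section 2.4 prefers intervals in general, and section 7.1.2 announces a supplementary SAP for secondary endpoints, which is not at hand. The plan also does not put an interval on every single-arm figure. Item 16 gives numbers and percentages of missed or falsely detected diagnoses without one, the number needed to examine under item 5 has none, and the compliance proportions in section 4 have none.

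Part of this stands. The contrast with section 7.1.2 holds for most proportions there, not for every figure, and the supplementary SAP might supply an interval. But section 2.4 names no safety output and does not override the explicit exclusions in 8.2 and 8.4. If only between-arm tests were meant, the text should say so.

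A reader might infer that the trial could not state what SAE risk its data exclude, or that risk would be hidden. The documents do not support that. The count and the denominator are both to be reported, each SAE is to be described individually, and the exact limit follows from count and denominator alone. Nor does the SAP give any SAE count: it says only that SAEs should be rare, so the zero-, one- and two-event cases above are scenarios.

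**Conclusion.** The point holds as a gap in reporting. Neither the lack of a comparison nor rarity justifies omitting a one-sample interval, and the omission is out of step with most intervention-arm proportions in the same plan.

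Its size, on the stated assumptions, is an unreported upper limit of about 0.23% for zero SAEs (0.19% to 0.30% over 1965 to 1250 tested) and 0.35% for one SAE. The swallow-failure rate is not given. A successful-swallow denominator would be somewhat smaller and its limit slightly wider.

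Adding the interval changes no point estimate and does not touch the primary endpoint. Reconciling the denominator and the counting rule may move the safety proportions themselves, and it has to be done for the interval to mean anything.

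**What to change.** Replace the exclusions in 8.2 and 8.4 with text to this effect:

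> No between-arm test of safety is planned. The proportions of participants with at least one AE, at least one severe AE and at least one SAE will be presented with 95% Clopper-Pearson confidence intervals; when the count is zero, the upper limit will be stated. The denominator is the safety population of section 3.2.4. A participant's events at the first and the repeat test both count.

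Bring sections 8.1 to 8.3 into line. Either adopt the section 3.2.4 denominator throughout, or label successful-swallow figures as a supplementary presentation. State that the SAE proportion counts participants rather than events.

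The cost is a short SAP edit and a few lines of code, using an exact method that section 7.1.2 already specifies. The one decision to settle first is the denominator and counting rule; an exact interval around a numerator that omits first-test events would look more precise than it is.

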8.3 Summary of Serious Adverse Events (SAE)

As for the above, SAEs will only be listed for responders of the Cytosponge™. They will be presented individually stating the participant ID, the event narrative, and the relationship with having undertaken the Cytosponge™.

An example of this is available in the DMC report from October 2018:

BEST3 SOP 008 – BEST3 Statistical Analysis Plan v1.0. [If this SAP has been printed or saved electronically, please check Sharepoint to ensure this version is the most up-to-date.](#)

CPTU Template Creating and Revising SOPs and other Guidelines v11.0 05/Jul/2019

[G:\EMS\CPTU\BEST3\Section 17 TRIAL COMMITTEES\Data Monitoring Committee \(DMC\)\Meetings \(agenda and minutes\)\4. DMC meeting - 30 October 2018\BEST3 DMC Report - Open - 30 October 2018.pdf](G:\EMS\CPTU\BEST3\Section 17 TRIAL COMMITTEES\Data Monitoring Committee (DMC)\Meetings (agenda and minutes)\4. DMC meeting - 30 October 2018\BEST3 DMC Report - Open - 30 October 2018.pdf)

Number/proportion of SAE (out of all successful swallows) will be reported.

